Exclusion criteria: Patients with plantar ulcer Patients with major foot deformity (e.g., Charcot foot, Pes Cavus) Patients with lower extremity amputation including minor amputation. Foot pain because of nail disorder or keratotic lesions (e.g. corns, calluses) Patients with unstable conditions (e.g., recent stroke, anticipated changes in medication regime) Acute fractures of the foot Participation in an interventional Study such as exercise intervention within the last 30 days Non-ambulatory or unable to stand without help or walk a distance of at least 6 feet without assistance. Patients with major cognitive impairment or major depression Patients who are unable or unwilling to participate in all procedures and follow up evaluations

F2. Procedure

7) The research will be conducted at the following location(s): Baylor College of Medicine and Baylor St. Luke's Medical Center (BSLMC). Duration of study: 12 weeks

Research staff may contact you for any study related questions throughout your participation in the study

Visit 1 (Baseline): Maximum duration 120 minutes

Screening: Measurements will take place at your home, or in Baylor Clinic based on your preference. Participants will be randomly placed in either Group A or Group B. Group A wears the OrthoFet shoes from baseline to 6 week follow up and Group B wears OrthoFet shoes from 6 week follow up to 12 week follow up.

All the same assessments and questionnaires are completed at each visit for all participants.

Foot Pain: Foot pain will be assessed by the revised Foot Function Index (FFI). FFI was developed in 1991 to measure the impact of foot pathology on function in terms of pain, disability, and activity restriction. It is a self-administered index consisting of 23 items divided into 3 sub-scales. Both total and sub-scale scores are produced. The FFI has been shown to be a reasonable tool for use with low functioning individuals with foot disorders, patients with rheumatoid arthritis, and non-traumatic foot or ankle problems. It can be used in both clinical and research settings. Foot pain will be assessed at baseline, week-1, week-6, week-7, and week-12.

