Postural Balance test: will be assessed in double stance and semi-tandem stance while subjects stand straight with hands crossed around the chest for up to 30 seconds with eyes open and closed. **Gait assessments:** A validated and FDA-approved wearable platform (LEGSysTM, Biosensics LLC) will be used to assess gait. Gait will be assessed over a distance of 20m using LEGSys, which uses five inertial measurement units attached to the anterior of each shin and, thigh, and posteriorly to the lower back. The system estimates spatiotemporal gait parameters such as stride velocity, stride length, stride time, double support, single support, and stride-to-stride variability, and gait initiation. In addition, the COM range of motion during walking will be calculated based on the data from the sensor attached to the lower back. Gait will be assessed under habitual speed and walking at maximum speed during a single task and dual-task condition.

Activities of daily living: ADL will be monitored using a validated pendant sensor (PamSysTM) during a period of one week at baseline (week-1) and week-6, and week-12. We used our validated algorithms to determine postures (lying, sitting, and standing postures), walking parameters (cadence, longest walking bout, total steps per day), sleep (time in bed, sleep efficacy, sleep onset latency), and activity behavior (sedentary, light, and moderate to vigorous activity) of each patient to monitor their performance. The algorithm for activity monitoring has been validated against direct observation, motion tracking system, as well as the patient diary. The algorithm for monitoring sleep was validated against Polysomnography and actigraphy in a sleep lab. The day-to-day reliability was also demonstrated in the geriatric population. In addition, we will use a Garmin wristwatch to track physiological stress response, daily activities, and sleep quality during the entire duration of the study. A pre-paid envelop will be provided to collect the sensor.

Quality of life and mobility: Health-related quality of life will be assessed using the Functional Assessment of Cancer Therapy - General (FACT-G) survey. General (FACT-G) is a 27-item questionnaire designed to measure four domains of quality of life: Physical, social, emotional, and functional well-being. Quality of life and mobility will be assessed at baseline, week 6 and week 12.

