We will utilize REDCap, a HIPAA compliant database application, to ensure uniformity of data entry. A qualified postdoc will provide ongoing oversight and reporting of data quality, including missing data, timeliness of data entry, responsiveness to data queries, etc. Data meetings will be held twice monthly, and specific challenges will be addressed. Baseline descriptive statistics among randomized groups will include demographic and clinical variables, summarized as mean (SD) (or median, IQR) for continuous variables and frequency (percent) for categorical variables. For each baseline variable, the magnitude of group differences will be summarized as pairwise standardized mean/proportion differences (group difference divided by SD). Distributions of continuous trial outcomes will be evaluated for normality; normalizing transformations will be completed if needed. Group comparisons on primary outcomes will be by intent to treat. Statistical testing on the outcomes will be evaluated at alpha=0.05 each. Group comparisons on secondary and exploratory outcomes will control for multiple comparisons (false discovery rate) using the Benjamini-Hochberg method. In all models, outcomes will be summarized as mean group levels (with 95% CI) and mean group differences (with 95% CI). Results of the user experience questionnaires will be calculated as median (range) for each Likert-scale question. Unpaired t-tests, Mann-Whitney u-tests, and Chi-square will be used for baseline between groups comparison to verify effectiveness of randomization. To evaluate the effect of gender as biological variable, we will examine whether acceptability and benefits of footwear (between groups as well as compared to baseline) are different between men and women.

Section H: Potential Risks/Discomforts

H1. Potential Risks/Discomforts

Describe and assess any potential risks/discomforts; (physical, psychological, social, legal, or other) and assess the likelihood and seriousness of such risks:

The risk to participants of this study is considered to be minimal in a controlled environment with an attendant present. This research routine will not place subjects at higher risk than normal activities of daily living, and no more risk of harm or discomfort is associated with these tests than the discomfort normally incurred while performing normal activities.

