Who will recruit subjects for this study?

PI

PI's staff

Describe how research population will be identified, recruitment procedures, any waiting period between informing the prospective participant and obtaining consent, steps taken to minimize the possibility of coercion or undue influence and consent procedures in detail.

Participants will be recruited based on referral from their clinician or through recruitment flyers placed in Baylor Clinic. The eligible subject will contact us or be approached by the research personnel after being referred by the clinical physician and his clinical staff (part of the research team). The subject will be fully informed about the study, and should voluntarily agree to participate with the guidelines as stipulated in the informed consent. The study coordinator or designee will introduce the study, present the written consent form, and spend as much time as necessary to ensure the potential subject completely understands the protocol. Emphasis will be placed on the voluntary nature of participation and the subject will be assured that his/her care will not be compromised in any way whether or not they choose to participate. The subject will be informed s/he can withdraw from the study at any time without loss of benefits. Consent forms will then be signed and dated by the subject and individual obtaining consent (PI, co-PI, study coordinator, or designee). Once written consent is obtained, the protocol may begin immediately or a follow-up appointment may be made. The individual (PI, co-PI, study coordinator, or designee & interns) obtaining consent will be given a thorough training of the process and go through several mock consent scenarios. The consent training consists of understanding the study and being able to fully explain it to the participant providing all pertinent information (procedures, risks, benefits, alternatives to participant), giving sufficient time to the participant to consider whether or not they would like to participate, and answer any questions which the subject may have. The training will have a strong emphasis on subject comprehension of the research study by asking open-ended questions to the subject.

The original documents (with signature) will be maintained per IRB policy. Any critical information will be sent for inclusion

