in the medical records, if it affects patient's wellbeing and any future treatment. A copy of signed consent form will be offered to the patient for personal records. Informed consent will be obtained prior to performance of any study procedures.

Are foreign language consent forms required for this protocol?

No

J3. Privacy and Intrusiveness

Will the research involve observation or intrusion in situations where the subjects would normally have an expectation of privacy?

No

J4. Children

Will children be enrolled in the research?

No

J5. Neonates

Will non-viable neonates or neonates of uncertain viability be involved in research?

No

J6. Consent Capacity - Adults who lack capacity

Will Adult subjects who lack the capacity to give informed consent be enrolled in the research?

No

J7. Prisoners

Will Prisoners be enrolled in the research?

No

Section K: Research Related Health Information and Confidentiality

Will research data include identifiable subject information?

Yes

Information from health records such as diagnoses, progress notes, medications, lab or radiology findings, etc.

Yes

Specific information concerning alcohol abuse:

No

Specific information concerning drug abuse:

No

Specific information concerning sickle cell anemia:

No

Specific information concerning HIV:

No

Specific information concerning psychiatry notes:

No

Demographic information (name, D.O.B., age, gender, race, etc.):

Yes

Full Social Security #:

Yes

Partial Social Security # (Last four digits):

No

Billing or financial records:

No

Photographs, videotapes, and/or audiotapes of you:

Yes

Identifiable biospecimens

No

Other:

No

At what institution will the physical research data be kept?

The physical research will be kept in our BCM offices housed in the McNair Building room B10.401.

How will such physical research data be secured?

Data will be kept in locked file cabinets that only the research team has access to.

At what institution will the electronic research data be kept?

Data will be kept locked on network computers in our BCM offices, under the password protected server.

Address: \\discovery1.ad.bcm.edu\\bcm-dept-icamp

Such electronic research data will be secured via BCM IT Services- provided secured network storage of electronic research data (Non-Portable devices only):

Yes

Such electronic research data will be secured via Other:

No

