Will there be anyone besides the PI, the study staff, the IRB and the sponsor, who will have access to identifiable research data?

Yes, identify the classes of the persons:

Yes, identify the classes of the persons: People who ensure quality from the institutions where the research is being done, federal and other regulatory agencies will have access to all of the research data.

Please describe the methods of transmission of any research data (including PHI, sensitive, and non-sensitive data) to sponsors and/or collaborators.

Transmissions, if any, will only happen via secure emails.

Will you obtain a Certificate of Confidentiality for this study?

No

Please further discuss any potential confidentiality issues related to this study.

NA

Section L: Cost/Payment

Delineate clinical procedures from research procedures. Will subject's insurance (or subject) be responsible for research related costs? If so state for which items subject's insurance (or subject) will be responsible (surgery, device, drugs, etc). If appropriate, discuss the availability of financial counseling.

All clinical/standard procedures will be billed to the subject's insurance. These include, physician visits, debridement, medications prescribed by physician.

There will be no research procedures charged to the subject or their insurance. This includes, the research device, materials provided by the research team, visits with the research team.

If subjects will be paid (money, gift certificates, coupons, etc.) to participate in this research project, please note the total dollar amount (or dollar value amount) and distribution plan (one payment, pro-rated payment, paid upon completion, etc) of the payment.

Dollar Amount:

135

Distribution Plan:

For taking part in this research, the subject may be paid a total of \$135. Their compensation will be broken down as follows:

Subjects will be paid \$25 for 3 in person visits, \$30 for every visit completed over the phone. There are a total of 5 visits. Payments will be done using the ClinCard method. Their SSN will be requested for the research team to issue the payments. The research study will also cover the subject's parking or transportation expenses to go to their research visits.

Section M: Genetics

How would you classify your genetic study?

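### The one-week pendant recordings are not tied to the shoe changes and no pre-shoe activity week is required for Group A, so change from baseline in activity may be biased

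*Combined protocol and SAP*

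**What the plan says.** Section F2 (Activities of daily living) sets the pendant schedule: "ADL will be monitored using a validated pendant sensor (PamSysTM) during a period of one week at baseline (week-1) and week-6, and week-12". No start or end day is given for any of the three weeks. The label *baseline (week-1)* joins two occasions that are separate elsewhere: F1 (Design) lists baseline and week 1 as different assessments, and F2 (Foot Pain) says "Foot pain will be assessed at baseline, week-1, week-6, week-7, and week-12".

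On the shoes, F2 (Visit 1) says "Group A wears the OrthoFet shoes from baseline to 6 week follow up". At Visit 3 Group A stops and Group B starts. By Visit 5 all shoes are back. The visits that give the recordings their names are therefore the visits at which the shoe condition changes.

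F1 defines the secondary outcome as change from baseline in daily activity metrics. Section G2 plans group comparisons on secondary outcomes, summarised as group means and mean differences. For the comparison of men and women it looks at benefit both between groups and against baseline. It names no crossover contrast.

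**The concern.** A change score needs a baseline recorded under the same condition in both groups. If the first pendant week follows Visit 1, Group A's baseline already contains whatever the shoes do in their first week, and Group B's does not. Section D sets out to look for an effect on daily activities at one week, so the plan cannot also assume that Group A's first shoe week is untreated.

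The two later weeks raise a second question. If they end at Visits 3 and 5 they capture the intended condition. If they start there, they capture the condition after the switch or after shoe return. What is at stake is the size, and in the worst case the sign, of the activity result.

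**Working it through.** **1. What the first recording week could be.** Two features favour the week after Visit 1. The same hyphen appears in week-6, week-7 and week-12, so it is unlikely to be a minus sign, and F1 and F2 (Foot Pain) use week 1 for the first week of follow-up. A week before the shoes would need an earlier contact, because "Informed consent will be obtained prior to performance of any study procedures" (J2). Section L says "There are a total of 5 visits", and these account for the whole stated payment: 3 x $25 + 2 x $30 = $135. None comes before Visit 1. On the other side, J2 also says "Once written consent is obtained, the protocol may begin immediately or a follow-up appointment may be made", which leaves room for a gap but links it to no recording.

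**2. Shoe status in the three recordings.**

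| Reading | Group A | Group B |
|---|---|---|
| 1. First week after Visit 1; later weeks end at Visits 3 and 5 | on, on, off | off, off, on |
| 2. Every week ends at its visit | off, on, off | off, off, on |
| 3. Every week starts at its visit | on, off, off | off, on, off |

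Reading 3 places the last recording in weeks 12 to 13, beyond the stated 12-week duration.

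**3. Formulas.** Let E be the six-week effect on a metric and k the share of E present in the first shoe week. The documents give no value for k, so it is assumed over 0 to 1. No carryover is assumed at first. Expected values in units of E (first week, week 6, week 12):

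- Reading 1: A = (k, 1, 0), B = (0, 0, 1).
  - A-minus-B change at week 6: (1-k) - 0 = 1-k.
  - On-shoe change averaged over A at week 6 and B at week 12, assuming no period effect: [(1-k) + 1]/2 = 1-k/2.
  - Difference in levels at week 6: 1-0 = 1.
  - Within-person contrast [(A6-A12) - (B6-B12)]/2 = [1-(-1)]/2 = 1.
- Reading 2: A = (0, 1, 0), B = (0, 0, 1). All of these equal 1, so there is no bias.
- Reading 3, with k also applying to Group B's first shoe week: A = (k, 0, 0), B = (0, k, 0).
  - Change at week 6: -k-k = -2k.
  - Difference in levels at week 6: -k.
  - Contrast: [0-k]/2 = -k/2.

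**4. Results, in units of E.**

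| k | Reading 1: A-B change, week 6 | Reading 1: averaged on-shoe change | Reading 1: level difference and contrast | Reading 3: A-B change, week 6 | Reading 3: contrast |
|---|---|---|---|---|---|
| 0 | 1 | 1 | 1 | 0 | 0 |
| 0.25 | 0.75 | 0.875 | 1 | -0.50 | -0.125 |
| 0.5 | 0.50 | 0.75 | 1 | -1.00 | -0.25 |
| 1 | 0 | 0.50 | 1 | -2.00 | -0.50 |

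**5. Carryover.** If a share c of the effect persists in Group A at week 12, the Reading 1 contrast is [(1-c) + 1]/2 = 1-c/2, for example 0.90 at c = 0.2.

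**6. Precision.** With 15% dropout, 50 x 0.85 = 42.5, so take 21 per group. Let V be the variance of a within-person difference, the same for every pair of occasions (equal correlation). The standard error of the week-6 A-minus-B change is sqrt(2V/21). That of the contrast is half of it, sqrt(V/42).

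**The case against.** The strongest reply is that the text calls the recording a baseline and sets it on the same baseline, week-6 and week-12 schedule as quality of life and the patient-reported outcomes. A 12-week study argues against a last recording after Visit 5; if that week ends at its visit, the first may too. The payment list does not exclude an unpaid consent contact or a mailed sensor. The label could also be a slip for two separate recordings. All this stands as far as it goes: a reader might infer that Group A's baseline is certainly recorded in the shoes, and the documents do not establish that. What they do show is that no pre-shoe activity week is required.

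A reader might also infer that the week-6 and week-12 recordings fall in the wrong shoe condition. That is not supported either. If week-1 means the first week, week-6 and week-12 would be the sixth and twelfth weeks, in the intended condition. The mail-back envelope fits wear after a visit but proves nothing. The windows are simply open.

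Third, G2 reports group levels, and under Reading 1 the randomised week-6 difference in levels is E whatever k is. This stands, so it would be wrong to say that the trial cannot estimate an activity effect. But F1 defines the outcome as a change from baseline, and the change is what is exposed.

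Finally, the Garmin is worn throughout and tracks daily activities. It helps for metrics that it captures. No pre-shoe Garmin week is stated, however, and standing, cadence and longest walking bout are described only for the pendant.

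**Conclusion.** The point holds in a limited form. The pendant weeks are not anchored to the shoe changes, and nothing secures an untreated activity baseline for Group A. On the more natural reading, the week-6 A-minus-B change from baseline is (1-k)E, given that later recordings precede Visits 3 and 5 and there is no carryover. Its size cannot be fixed from the documents: it runs from no bias at k = 0 to complete loss of the effect at k = 1. If every recording starts at its visit, the level difference and the within-person contrast fail as well.

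This is a cheap improvement to a secondary outcome in a 50-person proof-of-concept study. The primary pain outcome is a questionnaire and is unaffected. A reader might conclude that a run-in week is indispensable. It is not, because comparisons that need no baseline are available once the later windows are defined.

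**What to change.** By protocol amendment:

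- **Label.** Reconcile *baseline (week-1)* in F2 with the separate baseline and week-1 occasions in F1 and F2 (Foot Pain).
- **Windows.** Define the week-6 and week-12 pendant recordings as the seven days ending at Visit 3 and at Visit 5, before shoes change hands or are returned. The pendant must then be sent out before each visit: 2 x 50 = 100 mailings.
- **Analysis.** In G2, analyse daily activity by the within-person contrast of those two windows by sequence group. State its reliance on no carryover, and that its halved standard error assumes equal correlation between occasions. This costs text only, but it is valid only with the windows above.
- **First recording.** If it is made after Group A starts the shoes, call it week 1. Use it only for the one-week objective, as a between-group comparison of levels (expected value k - 0 = k, in units of E), and do not report change from it as a shoe effect.

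A pre-shoe recording week is optional. If the sponsor adds one, allocation should be made or disclosed after it, since F2 currently randomises at Visit 1, and a separate week-1 recording should be kept so that the one-week objective retains pendant data. The price is about one more week of participation, an extra recording, a later shoe hand-over for Group A, and a Visit 1 pain score about a week older at shoe start. No extra participants are needed. If the site already records before shoe start and before Visits 3 and 5, only the wording of the schedule changes.

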The study will be performed at the Baylor College of Medicine. Approval from Site Review Authority will be obtained. Subjects will be recruited from outpatient clinics at Baylor College of Medicine.

We propose a randomized crossover trial (Phase I/II) to evaluate acceptability as well as short (1 week) and intermediate (6 week) benefits and effectiveness of Orthofeet in reducing foot pain, increasing daily physical activities, and improving functional performance in ambulatory patients suffering from foot pain.

We are proposing a clinical study at the Baylor College of Medicine, to evaluate short and intermediate benefits and effectiveness of a novel pain relief footwear, called Orthofeet. This is a randomized crossed over trial. The duration of the study would be 12-week. We will recruit 50 eligible ambulatory adults (age 50 years or older) with moderate to severe self-reported foot pain. Participants will be randomly assigned to Group A (25 subjects) and Group B (25 subjects). There is no difference in assessments or eligibility between Group A and Group B, the only difference is when they have the opportunity to try the shoes for 6 weeks. Group A will receive a pair of Orthofeet shoes with adjustable insoles and will be asked to wear it every day activities of daily living for duration of six weeks. Participants will be also encouraged to wear the shoes inside of home if possible. Group B will be followed for duration of six weeks. At six weeks the groups will be switched and group B will receive a pair of Orthofeet shoes with adjustable insoles and Group B will follow-up for six weeks without Orthofeet shoes. Participants will be assessed at baseline, week-1, week-6, week 7, and week 12.

The primary outcome includes changes compared to baseline in foot pain intensity.

The secondary outcomes includes changes compared to baseline in various metrics of daily physical activities (e.g., daily step, longest walking bout, cadence, standing duration, and standing duration).

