Other outcomes include gait parameters (e.g., gait speed, gait steadiness, gait variability, double stance, and limp assessed using a validated wearable gait analyzer), static balance (assessed using a validated wearable balance assessment system), acceptability and perception of benefit (assessed by technology acceptance model), adherence (daily duration of wearing orthofeet), physiological stress response (e.g., heart rate variability, HRV, rest heart rate, HR-rest assessed by a wrist worn sensor), community engagement (life space assessed by a questionnaire). Standard questionnaires and assessments will be performed to evaluate subjects' perception of benefit, user-friendliness, satisfaction, adherence, pain, sleep quality, concerns for fall, frailty, moving ability, risk of falling, anxiety, and quality of life.

Resources available to conduct the Human Research

The PI is a Professor of Surgery at the Baylor College of Medicine and has been involved in multiple clinical trials along with numerous publications in the area of outcomes evaluation, foot care, pain management, physical activity monitoring, gait and balance assessments in relation to diseases such as diabetes, cancer, plantar fasciitis, and aging population. Other team members include biomedical engineers/research scientists and study coordinators who are well acquainted with the study site, culture, and society. The wearable sensor technology is available at our center (iCAMP) for this study and includes LegSys (to assess Spatio-temporal parameters of gait), BalanSens (to assess postural control) and PAMSys (to monitor daily physical activity pattern and behavior), and Garmin (to assess daily physical activities and physiological stress response). All persons assisting with the study have received appropriate training and are extremely knowledgeable in their study-related duties and functions.

Inclusion Criteria:

50 total subjects will be recruited. Those eligible will meet the following inclusion criteria: Male or female 50 years or older Self-reported foot pain including heel, arch, or ball of foot pain

Exclusion Criteria:

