Patient acceptability: We will use a Technology Acceptance Model (TAM) survey adapted for footwear to determine perceived benefit, perceived ease of use, acceptability, and attitude toward daily use. Patient acceptability will be assessed at the end of week 6 active use of OrthoFet (6- week for Group A and 12 week for group B) or the conclusion of the study for early endpoint.

Ancillary Measurements Patient-reported outcomes: Self-reported pain level will be extracted from FACT-G; ADL will be assessed using Katz Index of Independence in ADL; Community engagement will be assessed using the Life-Space Assessment questionnaire; The Fall Efficacy Scale-International (FES-I) questionnaire to determine concern for falls. Anxiety will be assessed using the Beck Anxiety Inventory questionnaire; cognition will be assessed using Montreal Cognitive Assessment (MoCA). Patient-reported outcomes will be assessed at baseline, week 6 and week 12. The subjects will not be advised or counseled based on the results of the questionnaires, these tools are not diagnostic, but the coordinators will try to provide possible resources if asked by the subject.

Digital Photographs , may take digital photographs of the subjects while performing exercise or during assessments for the purpose of publication (conferences/manuscripts). **Physical frailty:** Frailty will be assessed by trauma-specific frailty index and a validated wearable frailty meter technology.

Health related questionnaires: A series of health related questionnaires will be used to evaluate your quality of life , fear of falling, fall history, mobility, activities of daily living, depression, frailty, mental exams, foot examinations, pain intensity levels. Your medical history (from your clinic chart such as: medication use, prior surgery, diagnosis, progress notes, etc.) and demographic information will be obtained, such as age, gender, weight, and height. These questionnaires are asked to review the subject holistically and assess changes in their overall health, including mental and physical, over the 3 month span. The relevance to foot pain is to see how these components of health are related to foot pain such as finding a connection between their foot pain and fear of falling doing different activities.

At Visit 2 (1 Week Follow Up) the participant is called by the research staff to complete the pain questionnaire, document adverse events, and answer any study-related questions.

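### The only named quality-of-life instrument, which also supplies an ancillary pain level, is a cancer-therapy questionnaire, and one of two frailty measures is trauma-specific, in outpatients with foot pain

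*Combined protocol and SAP*

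**What the plan says.** In Section F2, the paragraph on quality of life and mobility names one instrument: "Health-related quality of life will be assessed using the Functional Assessment of Cancer Therapy - General (FACT-G) survey". It describes this as a "27-item questionnaire designed to measure four domains of quality of life: Physical, social, emotional, and functional well-being". The schedule follows: "Quality of life and mobility will be assessed at baseline, week 6 and week 12". Mobility appears in the paragraph's heading and in its timing sentence, but no tool is attached to it there.

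The ancillary measurements paragraph adds: "Self-reported pain level will be extracted from FACT-G". The physical frailty paragraph reads: "Frailty will be assessed by trauma-specific frailty index and a validated wearable frailty meter technology".

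The population is set in Section F1. The inclusion criteria are "Male or female 50 years or older Self-reported foot pain including heel, arch, or ball of foot pain", and the setting is given as "Subjects will be recruited from outpatient clinics at Baylor College of Medicine". No criterion refers to cancer. The only one that touches on injury excludes acute foot fractures.

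Foot pain itself is assigned in Section F2 to the revised FFI. The protocol says this covers pain, disability and activity restriction in three sub-scales, yields total and sub-scale scores, and is collected at baseline and weeks 1, 6, 7 and 12.

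**The concern.** An instrument designed around one patient group may ask about matters that do not change when a different group improves. Here the sole quality-of-life measure was built for people receiving cancer therapy, and the trial applies it to people given shoes for foot pain. If quality of life does not move, the trial cannot say whether the footwear had no effect on it or the questionnaire was looking elsewhere. Section G1 says the pilot is to lead to a Phase II proposal, so an uninterpretable result would carry forward into the choice of outcomes for that study.

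The pain level taken from FACT-G raises a separate problem. It gives a second self-reported pain reading beside a foot-specific one, and the protocol does not say which item supplies it or how a disagreement between the two would be read. The trauma-specific frailty index raises the same question of fit as the quality-of-life tool, on a smaller scale.

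**Working it through.** No figure in the plan bears on this point, so the check sets the instruments against the population and the other measures.

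| Outcome | Instrument named | Reason given for fit to this population |
|---|---|---|
| Foot pain (primary) | Revised FFI | Yes: use in foot disorders is cited |
| Daily activity (secondary) | PAMSys sensor | Yes: validation and reliability in older people are cited |
| Acceptability | Technology acceptance survey | Yes: adapted for footwear |
| Quality of life | FACT-G | None |
| Ancillary pain level | FACT-G, item not stated | None |
| Frailty | Trauma-specific index | None |
| Frailty | Wearable frailty meter | Described as validated |

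1. **Fit.** The protocol explains its choice for several measures but not for FACT-G or the trauma index. The mismatch is visible from the instruments' own names set against the entry criteria.

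2. **Pain.** The FFI is collected at 5 time points (baseline, weeks 1, 6, 7, 12). Patient-reported outcomes in the ancillary paragraph, including the FACT-G pain level, are collected at 3 (baseline, weeks 6, 12). All 3 are among the FFI's 5, so the extraction adds 3 − 3 = 0 new time points. The four domains listed for FACT-G do not name pain. That does not show the questionnaire lacks a pain item, but the protocol does not identify one.

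3. **Mobility.** The paragraph names no mobility tool, and none of FACT-G's four listed domains is mobility. Elsewhere Section F2 measures mobility by LEGSys gait testing, the PAMSys sensor and the Life-Space Assessment. What is missing is a named questionnaire source for mobility in this paragraph.

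4. **Frailty.** There are two tools. Removing the trauma index leaves the wearable meter, which Section P already lists as a study device.

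5. **Size.** The documents give no standard deviation, minimal important difference or responsiveness figure for FACT-G or the trauma index. The effect size in Section G1 (d = 0.50) is the planning value for change in foot pain and cannot be carried over to quality of life or frailty. The loss of sensitivity therefore has no computable value.

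6. **Reach.** Section F1 makes foot pain intensity primary and daily physical activity secondary. Neither uses FACT-G or the trauma index.

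**The case against.** The best defence is that these outcomes are peripheral. Quality of life appears in none of the hypotheses in Sections C and D, which concern pain, activity, gait, balance, heart rate variability and life space. Section F1 lists it among standard questionnaires, in a 50-person proof-of-concept study. The FACT-G pain level is labelled ancillary, so it already ranks below the FFI. As the protocol describes them, FACT-G's four domains are not peculiar to cancer. The warning in Section C that self-reported quality-of-life measures may be insensitive to change is aimed at conventional instruments in general, so it would also apply to a replacement.

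Most of this stands, and it sets the priority. The Section C warning cannot be used to argue that another questionnaire would be sensitive; it supports only careful selection. None of it supplies a reason for choosing a cancer or trauma instrument here, and the ancillary label does not say what the second pain reading is for.

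A reader might infer that mobility and frailty as a whole rest on these tools. The documents do not support that: mobility has the three other measures listed above, and the sentence that names the trauma index also names the wearable meter.

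**Conclusion.** The point holds as a minor one. A null quality-of-life result could not be told apart from a poorly targeted instrument, the FACT-G pain level duplicates a better-placed measure, and one of the two frailty measures is unexplained in this population. The primary outcome and the sensor-based secondary outcomes are unaffected.

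A reader might go further and infer that the trial would miss a real benefit, or that a footwear effect would shrink by some stated amount on these scales. The documents show only that this is possible. They reproduce no item wording and give no responsiveness data, so any attenuation figure would be pure assumption. Nor do they show how participants would respond to particular items.

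The conclusion rests on the instruments' names, the domains the protocol lists, the entry criteria and the absence of a stated rationale.

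**What to change.** Make three changes by amendment:

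- Replace FACT-G with a health-related quality-of-life instrument not built for cancer therapy that includes physical-function or mobility items. The quality of life and mobility paragraph would then have a named source for both.
- Delete the pain extraction from FACT-G, and state that self-reported foot pain comes from the FFI pain sub-scale only.
- Make the wearable frailty meter the frailty outcome, in place of the trauma-specific index.

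The cost is amendment text and replacement questionnaire forms, with no added visits or patients. The downside is lost comparability with any earlier FACT-G data the team may hold; the documents mention none.
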